This Appendix describes the continuation of the 3 Dynamic Prevention Randomized studies (refer to section 9.2.1 of protocol) for a 48 week follow up period following re-consent for this CAB-LA extension. Persons who are already enrolled in the trials and were randomized to the intervention arm will be eligible to receive CAB-LA as one of the options in the “Dynamic prevention” model. Persons in the control arms will be eligible to receive CAB-LA if and when it is rolled out through in country programs. If CAB-LA is not available in country at the 48-week endpoint, all participants in the intervention arm will have the opportunity to continue in the study until Week 96, and participants who are currently on CAB-LA may continue through the extension. The study will end at Week 96, and by that time participants will be transitioned to in country prevention care. At 96 weeks, persons on CAB-LA will be transitioned to in country CAB-LA or to other prevention options if CAB-LA is not available. Prior to this transition, available in country options will be assessed by the study team. HIV prevention options will be discussed with each study participant by their Week 88 visit, with a plan established for the transition to the participant’s preferred prevention method in coordination with local health facilities to avoid interruption after their 96 weeks of study participation is completed.

The overall purpose of this extension is to 1) Determine if adding the option of CAB-LA as a prevention choice using a patient-centered HIV prevention delivery model increases prevention coverage (i.e. proportion of time that is covered by a biomedical prevention option, such as PrEP or PEP) compared to the standard-of-care in 3 ongoing randomized trials of Dynamic Choice Prevention in rural Uganda and Kenya; and, 2) Conduct a hybrid implementation study (Primary Objective Clinical and Secondary Objective Implementation) focusing on initial implementation of a patient-centered model for CAB-LA using the RE-AIM evaluation framework among persons randomized to the intervention arms.

A. Background and Rationale

Background: SEARCH Sapphire is an ongoing, NIH-funded study that is testing multi-disease and multi-sector interventions aimed at reducing HIV burden and improving health in rural Uganda and Kenya. Phase A is a portfolio of randomized prevention and treatment implementation studies that will inform a population-level study in Phase B (refer to section 3.0 of protocol).

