This appendix describes a 48-week extension of 3 ongoing randomized trials in Phase A studying a patient-centered “Dynamic Choice Prevention” (DCP) implementation strategy for delivering existing evidence-based biomedical prevention interventions vs. standard of care (SOC). The Dynamic prevention model offers participants choices on prevention modality on an ongoing basis: oral PrEP, or oral PEP, and the option to switch between products. The trials are being conducted in 3 settings: antenatal (ANC) clinics, the outpatient department (primary care clinics), and in rural community settings in Western Kenya and Uganda (refer to section 9.2.1 of protocol). All clinic and village health team staff (i.e., Clinical Officers, nurses, coordinators, health workers) are trained and equipped for HIV prevention care in the clinical setting, appropriate to their role (refer to section 9.2.1.1 of the protocol).

In the CAB-LA extension, participants in the intervention and control arms are reconsented and remain in their initial randomized arm. Persons in the intervention arms who remain HIV

negative will be offered CAB-LA as an additional biomedical prevention option, if eligible. CAB-LA will be delivered at health clinics. The primary 48-week endpoint for this extension is proportion of time covered by a biomedical prevention product. As of May 9, 2022, a total of 1213 HIV-negative persons aged 15 years and older and at risk for HIV acquisition were enrolled in the studies. (Table 1). New participants are being enrolled at the present to time to replace those participants who have moved and have been unable to continue in the CAB-LA study. The total number of participants in the study eligible for CAB-LA will not exceed the 593 listed in Table 1.

Table 1. Enrollment in 3 SEARCH Sapphire Dynamic Prevention Trials as of May 9, 2022

Dynamic Prevention Study	Intervention and Control, (N) Uganda	Intervention (N) Uganda	Intervention and Control, (N) Kenya	Intervention (N) Kenya	Total Enrolled (N), Intervention and Control	Total Enrolled Intervention (N)
Antenatal/SRH Clinic	200	100	201	103	401	203
Outpatient Department Clinics	201	100	201	97	402	197
Household Study Community Village Health Team (VHT)	200	83	210	110	410	193
All Trials Together	601	283	612	310	1213	593

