At the time of writing of this protocol version, the standard of care for both Kenya and Uganda is to offer biomedical prevention as part of the HIV prevention package that includes provision of PrEP for persons at risk of HIV acquisition, such as persons with partners living with HIV or of unknown HIV status, or those with a history of exchange/transactional sex, recent STIs, or recurrent use of PEP (more than 3 times a year). PEP is offered primarily after occupational exposures or in cases of sexual assault. For participants consenting in the extension, in the control arm, they will continue to be seen by government staff in the HIV clinic or other service location, like a drop-in centre, and receive prevention interventions according to standard of care guidelines recommended by the country's Ministry of Health. There will be no change to their HIV prevention healthcare (refer to section 9.2.1.5 of protocol)

Control participants will be seen for a study visit every 24 weeks for HIV testing (RNA and rapid), weight, and a survey on which prevention method(s) they have been using and self-reported risk. If control participants report using medications such as PrEP or PEP at the interim visits, they will be asked to provide hair, blood, or urine samples in order to measure HIV prevention medication levels.

For intervention participants who do not choose CAB-LA, there will be study visits every 12 weeks (refer to section 9.2.1 of the protocol); however, they can decide to begin CAB-LA at any time during the initial 48-week extension. Participants will not be able to initiate or restart CAB-LA in the additional extension period between Week 48 and Week 96; only those who are taking CAB-LA at the time of the Week 48 visit may continue. Intervention participants that choose CAB-LA will have study visits that align with their injection visits (every 4 weeks for the first two months and then every 8 weeks thereafter), but can return to an alternate DCP intervention if they decide to stop CAB-LA.

For participants that select CAB-LA, the extension visits will also include (Table 6):

- A separate qualitative interview (At time of CAB-LA start, Week 24 and Week 48)
- Safety Labs:
 - HBsAg at baseline
 - ALT at Weeks 0 and 24; optionally at Weeks 8 and 48
- Pregnancy tests
- In addition to the Week 24 and 48 extension visits, injection visits will occur in clinic every 4 weeks for the first two months and then every 8 weeks thereafter

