The primary study endpoint in this extension will be biomedical covered time defined as the proportion of follow-up time that the participant is protected from HIV infection by any PEP or PrEP (inclusive of CAB-LA). Follow-up will be over the 48 weeks following re-consent for the CAB-LA extension. At risk covered time will be a secondary outcome, defined as the proportion of at-risk follow-up time that the participant is protected from HIV infection by any PEP or PrEP (inclusive of CAB-LA). We will also conduct sensitivity analyses, varying the definitions of coverage and risk. For example, we will also examine covered time from CAB-LA only (i.e., exclusive of oral PrEP or PEP), and we will conduct a sensitivity analysis in which we treat time after loss to follow-up among persons not known to have moved out of the study region and time after study withdrawal as presumed to be non-covered.

For our primary objective in this extension, we will compare covered time during the 48 week CAB-LA extension between the intervention and control arms. For improved efficiency, Targeted Maximum Likelihood Estimation (TMLE) will be used to adjust for differences in baseline participant characteristics between the two trial arms, accounting for the stratified randomization design. In secondary analyses, we will further use TMLE to i) adjust for measured differences between arms at time of start of the CAB-LA extension period; and, ii) adjust for baseline and time-varying factors that are predictive of the outcome and that differ between persons that do vs. do not have their follow-up time censored. The primary analysis will pool over the trials, accounting for clustering inherent in the community trial; secondary analyses will stratify by trial site. We will test the null hypothesis that covered time is the same between arms with a two-sided test at the 5% significance level.

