Costs will be estimated as the sum of the product of resources (e.g. staff minutes) times unit costs (e.g. compensation levels). “Economic” costs (the true value of resources consumed or “opportunity costs”) will be assessed by identifying the value of subsidized or donated resources with information from databases (e.g. wage rates) and donors. We will use prices prevailing at the time of study onset and will convert any locally incurred costs using the Kenya or Uganda Shilling / US dollar exchange rate at that time. Costs of CAB-LA implementation will be compared to the costs of oral PrEP implementation estimated during the primary trial to estimate the incremental cost of CAB-LA implementation.

Power and Sample size considerations

For each ongoing trial, we assume 90% of participants consent to the extension (reflecting the high retention in the ongoing trials seen to date). Of those, we assume 90% are retained through the extension. In the individually randomized ANC and OPD trials, we anticipate >80% power to detect a 11% or greater absolute increase in prevention coverage between arms with 162 participants/arm (assuming $\sigma = 0.35$). In the cluster-randomized community-based trial, we anticipate >80% power to detect a 15% or greater absolute increase in prevention coverage between arms with ~20 participants in each of the 16 clusters (assuming mean prevention coverage in the standard of care arm of 10%, $\sigma = 0.35$, and a matched-pair coefficient of variation $km=0.25$). These calculations are expected to be conservative given the ongoing enrollment and primary approach to conduct a pooled analysis as well as the increased precision from stratified randomization and through covariate adjustment with TMLE. Minimum detectable effect sizes varying these assumptions (including allowing for lower retention in either the ongoing or extension studies) are shown in Figure 4.

Figure 4. Minimum detectable effect sizes for the primary hypothesis

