All metrics will exclude persons who died, withdrew, or seroconverted by that week of follow-up. At week-48, we will additionally exclude persons who did not reconsent to the extension study (see NCT05549726 for details).

We will also characterize ever use of DCP intervention components over follow-up. We may also report on reasons for product changes, barriers to care, plans to address those barriers, and utilization of the phone hotline. We will report these metrics overall and within key subgroups, such as sex.

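### The CAB-LA extension's primary comparison covers only people who re-consent about a year after open randomisation, and no analysis listed in Appendix 18 H brings back those who do not

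*Protocol*

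**What the plan says.** Protocol Appendix 18 carries the three Dynamic Prevention trials forward. Part A states: "In the CAB-LA extension, participants in the intervention and control arms are reconsented and remain in their initial randomized arm". The primary endpoint is the proportion of time covered by a prevention product, and H. Analyses says of it: "Follow-up will be over the 48 weeks following re-consent for the CAB-LA extension". Parts B and C define the same clock. A person who never re-consents therefore has no start date and no extension follow-up.

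The offer differs by arm. The opening of the appendix says: "Persons who are already enrolled in the trials and were randomized to the intervention arm will be eligible to receive CAB-LA". For the others: "Persons in the control arms will be eligible to receive CAB-LA if and when it is rolled out through in country programs". Part D adds for controls that "There will be no change to their HIV prevention healthcare", and Part E asks them for two more visits, at weeks 24 and 48.

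The power section says "we assume 90% of participants consent to the extension" and that 90% of those are retained. It treats both as loss of sample size and gives no split by arm.

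Part H lists these analyses:
- a primary TMLE adjusting for baseline characteristics;
- secondary TMLE (i), adjusting for measured arm differences when the extension starts;
- secondary TMLE (ii), adjusting for baseline and time-varying factors related to censoring;
- a sensitivity analysis that counts as uncovered the time after loss to follow-up (unless the person is known to have moved away) and also takes "time after study withdrawal as presumed to be non-covered".

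Part C defines censoring as HIV diagnosis, death or withdrawal. The village health team (VHT) and outpatient SAPs (section 5) first remove people who died, withdrew or seroconverted from their implementation metrics, and then state: "At week-48, we will additionally exclude persons who did not reconsent to the extension study".

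**The concern.** Re-consent happens after randomisation, with arm known, and what a person gains by agreeing depends on the arm. It can therefore depend on both arm and interest in prevention. Once entry to the comparison rests on such a choice, randomisation alone no longer guarantees that the two analysed groups are comparable.

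Baseline adjustment and secondary analysis (i) act only on measured differences among people who entered. Secondary analysis (ii) and the sensitivity analysis act on follow-up that began and then stopped. None of them reaches people who declined before time zero. At stake is whether the result can be read as the effect of assignment in the three randomised trials, or only as a contrast among those willing to continue.

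**Working it through.** **Plan's own figure.** For an antenatal or outpatient trial: 200 × 0.90 re-consent × 0.90 retained = 162 per arm. With SD 0.35 and an 11-point difference, SE = 0.35 × √(2/162) = 0.0389 and 0.11/0.0389 = 2.83. Power = Φ(2.83 − 1.96) = 0.807 (0.805 with the t distribution). The stated power above 80% reproduces, so the issue is the analysis population and not the arithmetic.

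**Who is left out.** Part A, Table 1 gives 1213 enrolled: 593 intervention and 1213 − 593 = 620 control. Ten per cent is 59.3 + 62.0, about 121 people.

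**Scoring decliners as uncovered.** Difference = c1·r1 − c0·r0, where c is coverage among re-consenters and r is the re-consent rate (1 = intervention, 0 = control). Control coverage of 10% is the community-trial assumption, and 30% is the protocol's illustrative value for the clinic trials. The gap among re-consenters is set at 11 points. Power assumes 200 per arm and 90% retention of re-consenters. Only the overall 90% is documented; the arm-specific rates are assumptions.

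| Re-consent (interv./control) | 21% vs 10% | Power | 41% vs 30% | Power |
|---|---|---|---|---|
| 90/90 | 18.9 − 9.0 = 9.9 | 80% | 36.9 − 27.0 = 9.9 | 77% |
| 95/85 | 19.95 − 8.5 = 11.45 | 90% | 38.95 − 25.5 = 13.45 | 96% |
| 85/95 | 17.85 − 9.5 = 8.35 | 66% | 34.85 − 28.5 = 6.35 | 41% |

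The estimate can move either way.

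**Bias with no true effect.** Let both arms have mean coverage μ, and let decliners have mean a. Re-consenters then average (μ − (1 − r)a)/r, and the bias is the arm difference in that quantity.
- 90/90, intervention decliners at 0, control decliners at μ to 2μ: +1.1 to +2.2 points at μ = 10%, and +3.3 to +6.7 at μ = 30%. Pooled over the trials, with 90% retention and clustering ignored, type I error is about 0.08 to 0.17 and 0.32 to 0.85.
- 90/90, intervention decliners at μ, control decliners at 0: −1.1 (μ = 10%) or −3.3 (μ = 30%).
- 90/90, all decliners at 0: zero.
- 95/85, all decliners at 0: 10/0.95 − 10/0.85 = −1.2 (μ = 10%), or −3.7 (μ = 30%).

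**Why zero-scoring alone is not enough.** Take μ = 10%, 90/90, intervention decliners at 0 and control decliners still covered at 10%. Re-consenters average 11.1 and 10.0, a bias of +1.1. Scoring all decliners as 0 gives 0.9 × 11.1 − 0.9 × 10.0 = +1.0, so almost all of the bias remains. Giving control decliners their 10% adds 0.1 × 10 = 1.0 to that arm and the difference is zero. At 95/85 with the same decliner coverage, the bias among re-consenters is 10/0.95 − 10.0 = +0.5, and zero-scoring enlarges it to 10.0 − 8.5 = +1.5.

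**The case against.** The estimand is open: the hypothesis in Part B is itself stated over the 48 weeks after re-consent, and extension surveys cannot be given to people who decline. Part H calls itself an overview, introduces its sensitivity analyses as examples, and no extension SAP is among the documents supplied. Secondary analyses (i) and (ii) deal with measured selection among entrants and with censoring. At equal 90% re-consent, zero-scoring leaves power at about 80%. All of this stands, so this is a request for an additional analysis and not an error in the primary one.

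Study withdrawal might be read to include declining re-consent. That is strained: the follow-up definition gives decliners no time to score, and two SAPs list non-re-consent separately from withdrawal.

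A reader might also infer three stronger things that the documents do not support:
- *That the intervention arm is enriched for people who want a product.* If the CAB-LA offer raises intervention re-consent, that arm is less selected and the control arm more so.
- *That restoring decliners will usually make the result less favourable.* In the 95/85 case that this incentive suggests, zero-scoring raises 11 points to 11.45 or 13.45.
- *That the VHT and outpatient week-48 figures are inflated in the same way.* Those are disclosed, descriptive, intervention-arm-only metrics of the parent trials, and a denominator of continuing participants is defensible. The antenatal SAP stops these metrics at week 36.

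**Conclusion.** The point holds as a gap in the robustness analyses. About 10% of participants are expected to leave between randomisation and time zero, at a decision that arm can influence, and no listed analysis returns them. The documents do not establish the direction or size of any bias. The illustrative range of −3.7 to +6.7 points rests on assumed arm-specific re-consent rates and assumed coverage among decliners. Against a planned detectable effect of 11 points it is large enough to examine, but a much larger observed effect would survive it. Controls can obtain CAB-LA if national programmes supply it, so the asymmetry lies in the study's own offer. Entry also requires being HIV-negative and resident in the region when the extension starts, and new enrolees replace people who moved away. Any analysis of those randomised has to state how it treats these groups.

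**What to change.** In Appendix 18 H:

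1. Report re-consent by arm, with baseline characteristics and pre-extension covered time for those who did and did not re-consent.
2. Extend secondary TMLE analysis (ii) so that non-re-consent is handled as missingness, using baseline data and pre-extension covered time.
3. Extend the non-covered sensitivity analysis to all originally randomised participants who were alive, HIV-negative and not known to have left the region when the extension opened, with replacement enrolees kept separate. Score non-re-consenters as non-covered, and also vary their assumed coverage by arm as a tipping-point range, for example by carrying forward pre-extension coverage in controls, who can still use government services.

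As an optional minor addition, the VHT and outpatient SAPs could show both week-48 denominators.

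The primary analysis, visits and care are unchanged. Consent is already logged, and the parent trials' baseline and survey data already exist. The cost is some extra analysis, including a rule for replacement enrolees and for missing pre-extension coverage, and an estimate that may be more or less favourable than the primary one.

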- At each visit, signs and symptoms of acute HIV infection will be reviewed by study clinicians, including fever, diffuse rash, or swollen or enlarged lymph nodes. For patients suspected of having acute HIV, clinics will have access, provided by the study, for rapid viral load (using the Cepheid GeneXpert platform) if not available by the MoH, in order to ensure treatment of presumed HIV infection until test results return. The study will work with the MoH for partner notification in these cases to ensure completion and may also do social network outreach in order to identify and treat potential acute infection chains of infection.
- HIV seroconversion: For participants who are diagnosed with HIV in the course of the study, blood and hair samples will be collected for confirmatory HIV testing, drug resistance, and adherence measurement if indicated at the seroconversion visit and at 6 and 12 months. Patients will be referred to standard HIV care and treatment, including same-day ART start.

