-Hair sample (if CAB-LA received in last 120 days)			X		X	X		X						
-Stored plasma (from 2 cc sample above)		X	X	X	X	X	X	X						
Safety Labs														
-Pregnancy testing ¹	X	X	X	X	X	X	X	X	X	X	X	X	X	X
-ALT Monitoring ^{4, 5}	X		X*		X			X*			X*			X*
Adverse Event Monitoring	X	X	X	X	X	X	X	X	X	X	X	X	X	X
GBV Screening	X				X			X			X			X
Survey and IDI														
-Participant CAB-LA Survey and IDI ²	X				X			X						
-Provider and Clinic Staff DCP-LA Survey and IDI	X				X			X						
Costing³	X	X				X								
For participants who stop CAB LA before end of extension study														
-For 48 weeks from last injection: Recommend oral PrEP (TDF/3TC) to cover tail														
-Switch back to Q12 week visits - HIV RNA and pregnancy testing Q12 weeks														

¹For women who become pregnant, repeat pregnancy tests are not needed. Women who become pregnant during the study will be followed to delivery for assessment of mother and infant status

²Participant survey/IDI will be conducted at start of CAB-LA and Weeks 24 and 48 from time of CAB-LA start or discontinuation.

³Costing will occur between weeks 24-48.

⁴ALT Monitoring will occur at baseline, Week 24 for all participants. *Per provider discretion, ALT monitoring will occur at Weeks 8, 48, 72 and 96.

⁵Bilirubin and additional labs indicated will be tested in the case of ALT increase.

⁶HIV RNA will be drawn at CAB-LA reinduction, as described in Table 6.

⁷ Week 48 visits may occur between 40 and 56 weeks after Baseline; Week 96 visits may occur between 88 and 104 weeks after Baseline; only participants on CAB-LA at the Week 48 visit may take CAB-LA between weeks 48 and 96.

E. Extension Consent Process

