Any serious adverse event occurring in association with a pregnancy brought to the investigator's attention after the participant has completed the study and considered by the investigator as possibly related to the investigational product, must be promptly reported to NIAID and ViiV Healthcare.

Table 10. DAIDS Table for Grading the Severity of Adult and Pediatric Adverse Events

PARAMETER	GRADE 1 MILD	GRADE 2 MODERATE	GRADE 3 SEVERE	GRADE 4 POTENTIALLY LIFE-THREATENING
Clinical adverse event NOT identified elsewhere in the grading table	Mild symptoms causing no or minimal interference with usual social & functional activities with intervention not indicated	Moderate symptoms causing greater than minimal interference with usual social & functional activities with intervention indicated	Severe symptoms causing inability to perform usual social & functional activities with intervention or hospitalization indicated	Potentially life-threatening symptoms causing inability to perform basic self-care functions with intervention indicated to prevent permanent impairment, persistent disability, or death

General Criteria for Discontinuation of CAB-LA

Participants may voluntarily discontinue CAB-LA for any reason at any time. Investigators will permanently discontinue participants from CAB-LA per protocol for any of the specific

criteria below. Investigators also may permanently discontinue participants for reasons not shown here (e.g., to protect participants' safety and/or if participants are unable or unwilling to comply with CAB-LA use procedures).

The criteria for permanent discontinuation of CAB-LA use for an individual participant are:

- CAB-LA -related toxicity requiring permanent discontinuation per the guidelines above and below
- Request by participant to permanently terminate use of CAB-LA
- Clinical reasons determined by the Investigator
- Acquires HIV infection

CAB-LA will be temporarily withheld from a participant for any of the following reasons:

- Report of use of prohibited concomitant medications. CAB-LA injections may resume when the participant reports that he/she is no longer taking the prohibited medication, provided other reasons for temporary hold/permanent discontinuation do not apply.

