Our secondary objective to evaluate implementation will follow the RE-AIM framework and corresponding measures (defined in Table 4). Analyses assessing the primary measures of Reach, Adoption, Implementation and Maintenance will be based on standard descriptive statistics. Analyses to evaluate Effectiveness will compare covered time over the 48 week CAB-LA extension period to covered time prior to the CAB-LA extension among intervention participants. We will adjust for measured changes in participant characteristics between these two follow-up periods, using a TMLE designed for serial measures. Measures of control participants will also be used to adjust for temporal trends. We will test the null hypothesis that coverage of the DCP model with CAB-LA is the same as coverage of the DCP model without CAB-LA. We will again use a two-sided test at the 5% significance level. Primary analyses will again pool over trials, while secondary analyses will be stratified by trial. In addition, we will evaluate marginal and adjusted predictors of CAB-LA uptake and persistence. Our tertiary objective to evaluate changes in knowledge, awareness, and acceptability/satisfaction will be based on applying TMLE to survey data, accounting for repeated measures.

These analyses will be complemented with costing evaluations as well as participant and provider qualitative data from IDI.

All analyses of the community-based trial will account for clustering.

Pharmacokinetic analyses:

We will perform pharmacokinetic (PK) analyses of cabotegravir concentrations in plasma and small hair samples with two objectives. 1) To examine hair levels of CAB as predictors of effectiveness; 2) To examine factors associated with CAB PK variability and study correlations between CAB hair and plasma levels at the end of dosing intervals and during the PK tail. In the phase 3 trials of CAB LA, plasma concentrations of CAB did not fully explain CAB breakthrough infections (especially since failures occurred despite on-time injections) and therefore PK metrics, such as hair, that reflect longer-term exposure, may provide important insights regarding CAB exposure in addition to plasma. Drug concentrations of cabotegravir will be analyzed via liquid chromatography tandem mass spectrometry (LS-MS/MS) at the Hair Analytical Laboratory at UCSF. Plasma samples will be collected prior to each injection, while hair samples will be collected at weeks 8, 24, 32, and 48 after CAB LA start.

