First, we will analyze hair concentrations of cabotegravir in plasma and small hair samples as predictors of effectiveness. We will take the proximal 2 cm of hair from the scalp and segment the hair into two 1.0 cm segments (reflecting the prior two months of drug exposure in 1 month intervals), analyzing CAB levels in each segment. We will analyze hair levels from each collection visit from all participants who acquire HIV infection after starting CAB LA and three randomly selected controls who did not acquire HIV to compare exposure metrics from those for with and without HIV acquisition. We use sampling fraction weights to properly combine data from participants who acquire HIV (sampled with certainty) and controls in order to obtain accurate estimates for the entire study population.

Second, to examine factors associated with PK variability, we will perform univariate linear mixed effects regression using hair levels of CAB assessed as continuous outcomes with candidate predictor variables that may influence exposure, such as age, sex and body mass index (BMI), as well as plasma levels, and delays in injection visits. We will then build multivariate models to assess how associations with hair levels change when controlled for other factors. We will examine scatterplots and Spearman correlation coefficients between hair and plasma concentrations of CAB, including at the end of the dosing interval (using the hair concentration in the proximal 0.5 cm of hair since hair is collected before injections) and during the PK tail for participants who elect to stop CAB LA or who acquire HIV and start an oral ART regimen.

I. Analyses of In-Depth Interviews

Qualitative in-depth interviews will be conducted among purposively-selected samples of study participants and providers, to ascertain the perceptions of and experiences with CAB-LA use and delivery. Data will be analyzed using a framework analysis approach, wherein transcribed and translated data are inductively coded by a cross-regional team of trained qualitative researchers, the initial sets of findings are consolidated and grouped into conceptual categories, and a framework matrix is used to further condense findings tied most salient to the research questions.

[figure not shown]
J. Costing

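### The CAB-LA hair-level comparison of people who do and do not acquire HIV has no cut-off at infection and no alignment on time since injection, so stopping because of infection can look like low exposure before it

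*Protocol*

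**What the plan says.** The pharmacokinetic part of Protocol Appendix 18, section H, has two objectives. The one at issue is "To examine hair levels of CAB as predictors of effectiveness". For cases the rule is "We will analyze hair levels from each collection visit from all participants who acquire HIV infection after starting CAB LA". The comparison group is "three randomly selected controls who did not acquire HIV". On weighting it says: "We use sampling fraction weights to properly combine data from participants who acquire HIV (sampled with certainty) and controls".

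Four other places bear on which samples exist:

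- Section H sets CAB hair collection at weeks 8, 24, 32 and 48 after CAB-LA start. Each sample is the proximal 2 cm, cut into two 1 cm segments of about one month each.
- Section D, Table 6, counts weeks from the initial injection and takes hair only if CAB-LA was received within the previous 120 days.
- Section G has a list that opens "The criteria for permanent discontinuation of CAB-LA use for an individual participant are", and acquiring HIV is one of its items.
- Main Protocol 9.2.1.4 provides, for people diagnosed with HIV during the study, blood and hair for confirmatory testing, drug resistance and "adherence measurement if indicated at the seroconversion visit and at 6 and 12 months".

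Section H also plans hair-plasma correlations during the drug tail, including in people who acquire HIV and move to oral ART. The plan therefore expects some hair from cases after they stop CAB-LA.

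**The concern.** A predictor of infection has to be measured before infection. Once a case is diagnosed, CAB-LA stops and later hair shows a falling level. That fall is a result of the infection. If those samples are pooled with the earlier ones, cases can show lower cabotegravir than controls even when level had no bearing on acquisition.

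Timing is a related problem. A case diagnosed at week 16 has only the week-8 sample before diagnosis, while a control drawn at random can contribute all four weeks. Any change in hair level with time on drug would then appear as a difference between cases and controls. The sampling-fraction weights correct for which people are chosen; they do nothing about when the hair was taken.

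The appendix motivates hair testing by noting that plasma levels left some breakthrough infections in the phase 3 trials unexplained, including some with on-time injections. A spurious finding of low exposure in cases would mislead on exactly that question. The documents give no expected number of infections. With at most 593 people eligible for CAB-LA, cases are likely to be few, so one misplaced sample per case can matter.

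**Working it through.** The documents give no sample size, effect size or decay rate for this analysis, so there is no stated figure to reproduce. The check crosses the two schedules and then sizes the distortion.

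**Step 1: which samples fall after diagnosis.** Inputs are the injection weeks in Table 6 (0, 4, 8, then every 8 weeks), hair weeks 8, 24, 32 and 48, the 120-day condition, and a hair window of about 8 weeks. Assumption: infection is found at the injection visit after the last injection. Days since last injection = 7 × (hair week − last injection week). Share of the window after diagnosis = (hair week − diagnosis week) / 8, capped at 1.

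| Last injection (wk) | Diagnosis (wk) | Hair visits up to diagnosis | Later hair visit within 120 days | Window after diagnosis |
|---|---|---|---|---|
| 0 | 4 | none | 8 (day 56) | 50% |
| 4 | 8 | 8 | none (week 24 is day 140) | n/a |
| 8 | 16 | 8 | 24 (day 112) | 100% |
| 16 | 24 | 8, 24 | 32 (day 112) | 100% |
| 24 | 32 | 8, 24, 32 | none (week 48 is day 168) | n/a |
| 32 | 40 | 8, 24, 32 | 48 (day 112) | 100% |
| 40 | 48 | 8, 24, 32, 48 | none | n/a |

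Four of seven diagnosis times give one post-diagnosis sample, and none gives more than one. Late visits or a different injection calendar would move these counts.

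**Step 2: how low that sample reads.** Assume levels fall with a half-life h of 25 to 50 days (assumption; the documents give none). Relative to an on-schedule day-56 trough, f = 2^(−(112 − 56)/h).

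- h = 25: f = 2^(−2.24) = 0.21
- h = 50: f = 2^(−1.12) = 0.46

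**Step 3: effect on the case's average.** Suppose cases and controls have equal levels while on drug, so the true ratio is 1. A case with k hair visits, one of them after stopping, has a geometric mean ratio of f^(1/k).

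| Last injection (wk) | k | Ratio, f = 0.21 | Ratio, f = 0.46 | Deficit |
|---|---|---|---|---|
| 8 | 2 | 0.46 | 0.68 | 32-54% |
| 16 | 3 | 0.60 | 0.77 | 23-40% |
| 32 | 4 | 0.68 | 0.82 | 18-32% |

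The direction does not depend on the half-life. For last injection at week 16, a post-stop sample at 75%, 50% or 25% of the on-drug level gives ratios of 0.91, 0.79 and 0.63.

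**Step 4: with the cut-off.** If case hair stops at diagnosis and controls are read at the same weeks, the no-effect ratio is 1.00 by construction.

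**The case against.** Much can be said for the plan. Hair is cut into monthly segments, so samples taken by diagnosis mostly reflect exposure before it. Weeks are counted from the first injection for everyone, so a same-week comparison is possible with these data. Tail hair from people who acquire HIV has its own objective. Sampling all cases with weighted random controls is a recognised design. Section H calls itself an overview, and the pharmacokinetic work is not among the appendix's primary, secondary or tertiary objectives. All of this stands, and it limits the size and importance of the point. It does not supply the missing rule: the text for the predictor objective takes every collection visit and states neither truncation nor alignment.

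Three stronger readings are tempting but not supported:

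- A reader might infer that the 6- and 12-month samples in 9.2.1.4 enter this comparison. With the same assumed half-lives, a sample at day 182 would read 3-17% of a day-56 trough (2^(−126/25) to 2^(−126/50)). However, section H defines the CAB hair visits as weeks 8, 24, 32 and 48, a day-182 sample would fail the 120-day condition, and the 9.2.1.4 samples are taken only if indicated. The extension's own seroconversion sampling figure is not shown. These samples may add to the problem; the text does not say that they do.
- A reader might infer that controls are all still being injected. The text requires only that they did not acquire HIV. Participants may stop at any time, so controls can also contribute off-drug hair.
- A reader might infer that only risk-set sampling would be valid. Truncating randomly sampled controls at the matching week would also do.

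**Conclusion.** The concern holds in a limited form. Followed as written, the predictor analysis can include one scheduled post-diagnosis sample per case at 4 of 7 diagnosis times. In three of those the sample carries no pre-diagnosis exposure. In those three, the case's geometric mean falls by about 18-54% with no true effect. At the three diagnosis times with no qualifying sample this bias is absent, so the bias in the pooled comparison depends on when infections occur.

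The counts rest on Table 6 visit timing and on diagnosis at the next injection visit. The percentages rest on the assumed 25-50 day half-life, on equal levels at all on-drug visits, and on controls being on drug at the compared weeks. Control hair taken after stopping would narrow the gap. The size of the separate distortion from unaligned weeks cannot be computed from the documents.

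A reader might take this as a threat to the trial's main result. It is not: the primary covered-time comparison makes no use of cabotegravir hair levels. The change is still worth making, because it removes a real bias using data already collected.

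**What to change.** Amend the pharmacokinetic text in Appendix 18, section H, for the predictor objective:

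- Use only case hair segments grown before the estimated infection date, placed between the last negative and first positive HIV test. The rapid tests at each CAB visit, the scheduled HIV RNA tests and the stored plasma can support the dating.
- Compare with controls still HIV-negative at the same week since first injection, either by risk-set sampling or by truncating randomly sampled controls at that week. Compute the weights to match the method chosen.
- Account for days since last injection where late injections are not themselves the exposure of interest.
- State whether three controls means three per case or three in total.
- Report post-infection hair only under the tail objective, and say explicitly whether the 9.2.1.4 samples are used there.

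No new samples are needed. The cost is fewer usable samples per case: a case diagnosed at week 4 would contribute none, and one diagnosed at week 8 or 16 at most the week-8 sample.
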